7.5 DATA SOURCES

The data source for this project will be a combination of claims data from United Healthcare, a large national commercial health insurer, and MarketScan, a research claims database from commercial employer-sponsored health plans from July 2008 through December 2012 for the first interim report, with 6-month updates through December 2015. Data from July 2008 through September 2010 will be used for DRS estimation (see Main Analysis Section (6.9.1) for more details) while data from October 2010 will be used for cohort formation and analysis. Because of a 6-month time lag before data become available for United and 9-month time lag for MarketScan, we will not have access to any information beyond December 2012 for the first interim report.

1

We have obtained the following preliminary estimates from the UnitedHealth and MarketScan databases regarding the number of patients initiating dabigatran or warfarin (new users) and meeting the main study selection criteria in the period October 2010 – June 2012.

Table 7 UnitedHealth and MarketScan databases, estimated numbers of dabigatran and warfarin with non-valvular atrial fibrillation diagnosis, in the period October 2010 – June 2012

Medication	United Healthcare	MarketScan	Total
Dabigatran	4,150	20,000	24,150
Warfarin	7,720	40,000	47,720

7.6 BIAS

Various design and analysis methods will be implemented to reduce the potential for bias in the study. We will employ new-user cohorts of NOAC medications and warfarin in order to address differences that might arise in the comparison of newer and older treatments, such as survivor bias and attrition of susceptibles. The comparator cohort will be formed from warfarin initiators with similar clinical profiles to dabigatran and other NOAC medications initiators to reduce confounding by indication. We will employ propensity score matching of NOAC/dabigatran and warfarin cohorts in order to improve the balance of the cohorts with respect to numerous variables and will further assess the balance across the matched cohorts on the basis of disease risk scores for the primary outcomes. We will use established

algorithms for outcome identification and only outcomes expected to be ascertained well in insurance claims.

7.7 STUDY SIZE

The ability of this research program to detect a given risk increase depends on the incidence of the outcome as well as the number of cohort entrants and duration of follow-up. The study size will depend on the number of dabigatran (or other NOAC medications) and warfarin initiators who meet the study inclusion and exclusion criteria and are successfully matched into cohorts. On the basis of the outcome incidence rate observed in the comparison group in the pilot phase of this project (Phase 1) and the cumulative person-time of observation over the study period, we estimated the minimum relative rate that can be detected with 80% power for dabigatran-warfarin comparison.. During the period October 2010 – June 2012, among patients with a minimum of 12 months baseline history, no prior use of any anticoagulants, and a diagnosis of non-valvular atrial fibrillation, there are 4,158 dabigatran incident users in the UnitedHealth database and approximately 20,000 dabigatran users in MarketScan database. These dabigatran users will be matched to a similar number of warfarin incident users. Assuming that approximately 70% of patients will be matched, an average follow-up of 5 months (both based on the preliminary results from Phase 1 of the BI/ Pradaxa project) and the additional users who initiated dabigatran during July-December 2012 period, there should be slightly more 10,000 person-years of dabigatran follow-up for the initial analysis. As this project expands in 6 month increments, the person-time, along with outcomes and the ability to detect a particular relative risk will increase.

The table below provides estimates of the minimum relative rates that can be detected with 80% power for the major study outcomes under specific assumptions regarding their incidence in the comparator group (labeled “base rate”) and the accrual of person-time. The base case incidence rates are the rates observed in warfarin initiators who were calendar quarter- and PS- matched to dabigatran initiators during the October 2010-June 2012 period in the UnitedHealth database (Phase 1 of the project). We conservatively assumed that the number of patients initiating dabigatran each month during July 2012 – December 2015 is equal to the average monthly number of initiators during the first half of 2012, that at least 2/3 of these patients are matched 1:1 to comparator patients, and that each patient contributes 0.41 years of follow-up time.

Table 8 Projected minimum detectable relative rates* by reporting period

	Phase 1 (NOAC Cohort)	Interim report 1	Interim report 2	Interim report 3	Interim report 4	Interim report 5	Interim report 6	Final report
Report Date		Apr, 2014	Jul, 2014	Nov, 2014	Mar, 2015	Sep, 2015	Mar, 2016	Dec, 2016

Table 8 (con't) Projected minimum detectable relative rates* by reporting period

Data through (MarketScan/ United)	Jun, 2012	Dec, 2012	Jun, 2013	Sep/Dec, 2013	Dec 2013/Jun , 2014	Sept/Dec, 2014	Dec 2014/Jun , 2015	Dec, 2015
Estimated number of matched patients		24,000	30,000	36,000	42,000	48,000	54,000	60,000
Cumulative person-time of observation		10,000	12,350	14,700	17,050	19,400	21,750	24,100
Outcome	Base rate †	Minimum detectable relative rate						
Stroke	31.59	1.24	1.21	1.19	1.18	1.17	1.16	1.15
Major Hemorrhage	66.72	1.16	1.14	1.13	1.12	1.11	1.11	1.10
Ischemic stroke	32.71	1.23	1.21	1.19	1.17	1.16	1.15	1.15
Hemorrhagic stroke	2.09	1.87	1.77	1.70	1.64	1.60	1.56	1.53
MI	14.73	1.35	1.32	1.29	1.27	1.25	1.23	1.22
Major GI bleeding	31.63	1.24	1.21	1.19	1.18	1.17	1.16	1.15
Hepatotoxiciti ty	4.20	1.70	1.62	1.57	1.52	1.49	1.46	1.43

* This table reports the minimum relative rate that can be detected with 80% power assuming an alpha level of 0.05 and a 2-sided test.

† Base rate is incidence rate per 1,000 Person-Years observed in warfarin initiators matched to dabigatran during the October 2010-June 2012 period in the UnitedHealth database

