7.4.2 OUTCOME(S)

The primary outcomes of interest include stroke (hemorrhagic, ischemic, uncertain classification) and major bleeding. Secondary outcomes are: stroke or systemic embolism, , transient ischemic attack (TIA), myocardial infarction (MI), venous thromboembolism (VTE), deep vein thrombosis (DVT), pulmonary embolism (PE).

Systemic embolism (defined as an acute vascular occlusion of the extremities or any organ, such as kidneys, mesenteric arteries, spleen, retina or grafts), ischemic stroke, hemorrhagic stroke, stroke of uncertain classifications, major intracranial bleeding, major extracranial bleeding, major gastrointestinal (GI) bleeding, major upper GI bleeding, major lower GI bleeding, major urogenital bleeding, major other bleeding. Further outcomes include hepatotoxicity and all-cause mortality.

As mortality data in the commercial databases is currently limited to inpatient deaths, we will seek to improve the ascertainment of the death outcome through external linkage, such as with the Social Security Death Master File.

Table 2 **Outcome Definitions**

Outcome	Hospital Discharge Code(s)	Comments
Primary Outcomes		
Stroke	As primary ICD-9 discharge diagnosis (Dx): 431.x Intracerebral hemorrhage (ICH) 433.x1 Occlusion and stenosis of precerebral arteries with cerebral infarction 434.x1 Occlusion and stenosis of cerebral arteries with cerebral infarction 436.x Acute, but ill-defined cerebrovascular events	See Mini-Sentinel report for PPV for individual codes or other algorithms [R14-0052]
Major hemorrhage	Major intracranial bleeding, major extracranial bleed (for codes see component outcomes below)	
Secondary outcomes		
Stroke or systemic embolism	Stroke or systemic embolism (for codes see component outcomes below)	

Table 2 (con't)

Outcome Definitions

Outcome	Hospital Discharge Code(s)	Comments
Systemic embolism	ICD-9 Diagnoses: 444.x Arterial embolism	No validation studies available. Codes are thought to be specific because of the substantial clinical symptomatic and required therapy.

Table 2 (con't) Outcome Definitions

Ischemic stroke	As primary ICD-9 discharge diagnosis (Dx): ICD-9 Dx 433.x1 Occlusion and stenosis of precerebral arteries with cerebral infarction ICD-9 Dx 434.x1 Occlusion and stenosis of cerebral arteries with cerebral infarction	PPV 95.5% in commercially-insured population for the codes in any position [R11-4887] Use of codes in the primary position generally increases the PPVs [R14-0052]

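### Table 8: the hemorrhagic-stroke detectable rates (1.87 to 1.53) do not follow from the printed base rate of 2.09, and the ischemic-stroke base rate exceeds the all-stroke base rate

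*Combined protocol and SAP*

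**What the plan says.** Table 8 in section 7.7 gives, for seven outcomes, a base rate and the smallest detectable relative rate at each of seven reports. Its footnote states: "This table reports the minimum relative rate that can be detected with 80% power assuming an alpha level of 0.05 and a 2-sided test".

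The three stroke rows begin as follows (base rate per 1,000 person-years, then the detectable rate at Interim report 1):

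- "Stroke 31.59 1.24"
- "Ischemic stroke 32.71 1.23"
- "Hemorrhagic stroke 2.09 1.87"

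The hemorrhagic-stroke row continues 1.77, 1.70, 1.64, 1.60, 1.56 and 1.53.

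All base rates are given one source. The second footnote says "Base rate is incidence rate per 1,000 Person-Years observed in warfarin initiators matched to dabigatran", in UnitedHealth, October 2010 to June 2012. The text of section 7.7 agrees: "The base case incidence rates are the rates observed in warfarin initiators who were calendar quarter- and PS- matched to dabigatran initiators".

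Table 2 in section 7.4.2 defines Stroke by primary discharge diagnosis, starting with "431.x Intracerebral hemorrhage (ICH) 433.x1 Occlusion and stenosis of precerebral arteries with cerebral infarction" and adding 434.x1 and 436.x. Ischemic stroke, also by primary discharge diagnosis, is "ICD-9 Dx 433.x1 Occlusion and stenosis of precerebral arteries with cerebral infarction ICD-9 Dx 434.x1 Occlusion and stenosis of cerebral arteries" with infarction. Every ischemic-stroke code is therefore also a stroke code.

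**The concern.** Two things in the stroke rows do not fit together.

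1. Hemorrhagic stroke is the rarest outcome in the table, with half the base rate of hepatotoxicity (2.09 against 4.20). Its detectable rates looked too small for so few events.
2. A component has a higher rate than the composite that contains it.

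Table 8 is the protocol's only numerical statement of what the study can detect. If the hemorrhagic-stroke row is too favourable, a null result for that outcome would be read as more reassuring than it is. If the stroke base rates are inconsistent, either the rate for a primary outcome or the rate for its main component is wrong, or it was obtained under a definition other than the one this protocol will use.

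**Working it through.** **Inputs.** Two-sided alpha 0.05 and 80% power (Table 8 footnote). Person-years: 10,000; 12,350; 14,700; 17,050; 19,400; 21,750; 24,100 (Table 8), which apply to each group (protocol abstract, expected study size). Matching is 1:1 (section 7.7). Base rates are from Table 8.

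**Formula.** The documents name none. With E = base rate × person-years / 1,000 expected warfarin events and z = 1.960 + 0.842 = 2.802, the square-root two-rate formula is

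RR = (1 + z × √0.5 / √E)²

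**The rows that reproduce.** For stroke at Interim 1, E = 31.59 × 10 = 315.9 and RR = (1 + 1.981/17.77)² = 1.235 (printed 1.24). At the final report the formula gives 1.149 (printed 1.15). Across the six rows other than hemorrhagic stroke, 41 of 42 cells match to two decimals. The exception is hepatotoxicity at Interim 2 (1.626 against 1.62, a gap of 0.006).

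**Hemorrhagic stroke.** At Interim 1, E = 2.09 × 10 = 20.9 and RR = (1 + 1.981/4.572)² = 2.05. The full row:

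| Report | Printed | Formula at 2.09 | Formula at 2.90 |
|---|---|---|---|
| Interim 1 | 1.87 | 2.054 | 1.871 |
| Interim 2 | 1.77 | 1.932 | 1.772 |
| Interim 3 | 1.70 | 1.843 | 1.699 |
| Interim 4 | 1.64 | 1.774 | 1.643 |
| Interim 5 | 1.60 | 1.719 | 1.598 |
| Interim 6 | 1.56 | 1.674 | 1.561 |
| Final | 1.53 | 1.636 | 1.530 |

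None of the seven cells matches at 2.09; all seven match at 2.90. Base rates from 2.88 to 2.93 are consistent with all seven rounded cells under this formula, and 2.79 to 3.08 across the four formulas considered here.

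**Is it the choice of formula?** At 2.09 the other three give:

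- log rate ratio: 2.105 to 1.649
- rate difference: 2.075 to 1.642
- events-based (Schoenfeld): 2.024 to 1.628

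A one-sided Schoenfeld calculation gives 1.90 to 1.55, which still misses and breaks the other rows. Doubled person-time and 70% or 75% power do not yield the row either.

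**Power at the printed values if 2.09 is right.** Power = Φ(√(2E) × (√RR − 1) − 1.960). At Interim 1 this is Φ(6.465 × 0.3675 − 1.960) = Φ(0.416) = 0.66; at the final report it is also 0.66. The four formulas range from 0.64 to 0.68, and a Poisson simulation gives 0.66.

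**Size in events and person-time.** Expected warfarin-group events at the final report are 2.09 × 24.1 = 50.4, or 2.90 × 24.1 = 69.9. To detect 1.53 at a base rate of 2.09, E must be (1.981 / (√1.53 − 1))² ≈ 69.9, so about 33,400 person-years per group (32,800 to 34,300 across formulas) against the planned 24,100.

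**Component against composite.** In one cohort, a first-event composite counts at least as many patients with an event as any component, over no more person-time, so its rate cannot be lower. Table 8 has 32.71 − 31.59 = 1.12 per 1,000 person-years in the wrong direction (32.71/31.59 = 1.035). The effect on the stroke row is small:

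| Stroke base rate | Interim 1 | Final |
|---|---|---|
| 31.59 (printed) | 1.235 | 1.149 |
| 32.71 (strict floor) | 1.231 | 1.146 |
| 34.80 (= 32.71 + 2.09, no patient with both) | 1.224 | 1.141 |

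**The case against.** No formula was found that rescues the hemorrhagic-stroke row. The objections bear on the rest.

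- **Phase 1 definitions are not visible.** The base rates come from a separate protocol (1160.157, section 5), and nothing says it used the Table 2 codes, diagnosis positions or exclusions. This stands: the reversal is impossible only if Table 2 applied. But Table 8 states no difference, and an unstated one would mean that the base rate for a primary outcome does not describe the outcome to be analysed.
- **A simple typing error in 31.59 or 32.71 is unlikely.** Both rows reproduce in all seven cells from their own base rates, and they differ where they should (Interim 4: 1.178 and 1.175, printed 1.18 and 1.17). This also stands. It points to differing definitions, an error upstream of the table or mislabelled rows, and leaves the inconsistency in place.
- **Little depends on it.** Hemorrhagic stroke alone is not a primary outcome. Study size is set by eligible initiators and data releases, so 33,400 person-years is a measure of the discrepancy and not a shortfall against a target. No data cut or analysis uses the row. All true, and it limits the severity.
- **The base rate is fragile either way.** Phase 1 follow-up is not stated. Assuming 4,158 UnitedHealth users, 67 to 70% matched and 0.41 to 0.42 years each, it is about 1,140 to 1,210 person-years. Then 2.09 is about 2.4 to 2.5 events, 2.90 about 3.3 to 3.5, and the ischemic excess about 1.3 to 1.4. Correcting the entry makes the table consistent, not precise.

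**Conclusion.** Both points hold, and the table should be corrected.

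The hemorrhagic-stroke row is internally wrong: either the base rate or all seven detectable rates are in error. If 2.09 is right, the detectable rate is understated by about 0.18 at Interim 1 (2.05 against 1.87) and 0.11 at the final report (1.64 against 1.53), with power near 66% at the printed values. If the detectable rates are right, the base rate should be about 2.9. A dropped or inserted digit would explain the pattern, but the documents cannot confirm it. The conclusion assumes that this row was meant to use the same method and person-time as the other six; it does not depend on which standard two-sided formula is chosen.

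The stroke and ischemic-stroke base rates are incompatible with Table 2 in the single cohort that the footnote names. This rests on Phase 1 having used the same nested definitions. The size is 1.12 per 1,000 person-years (3.5%), with at most about 0.01 on the stroke detectable rates.

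Neither point affects the design or the analysis.

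**What to change.** 1. Check the Phase 1 event counts and person-years for hemorrhagic stroke. Correct either the 2.09 or all seven detectable rates.
2. Recompute the Stroke and Ischemic stroke base rates with the Table 2 definitions, so that Stroke is no lower than either component. If Phase 1 used other definitions, say so in a footnote and give them.
3. State the power formula under Table 8, recompute the affected rows with it, and reissue the table.

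The cost is one corrected table and a footnote. The stated sensitivity for hemorrhagic stroke may become less favourable. Data, design and analysis stay as they are.

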5. RATIONALE AND BACKGROUND

A number of new oral anticoagulants are being developed and marketed to replace vitamin K antagonists, one of the most important drugs in modern medicine. [P11-11875] Unlike vitamin K antagonists, these new drugs do not require dose titration involving intensive therapeutic monitoring of prothrombin time to achieve target anticoagulation within a narrow therapeutic range. In Phase III studies, these drugs were found to be therapeutically advantageous or non-inferior over warfarin. In the coming years, as many as six new anticoagulants could be on the market and a lack of valid comparative evidence will hinder prescriber and payor decision-making.

To date, these drugs have been studied in randomized clinical trials for three separate indications: (1) prevention of stroke and systemic embolism among patients with atrial fibrillation; (2) prevention of deep venous thrombosis (DVT) among patients undergoing hip or knee replacement therapy; and (3) treatment of venous thromboembolism (VTE). Phase III clinical trials comparing dabigatran, rivaroxaban, apixaban, and edoxaban to warfarin in patients with non-valvular atrial fibrillation (NVAF) have been completed. [R11-4190] [P09-11669] [R11-4223] [R13-5082] The objective of this part of the project is to conduct a series of comparative effectiveness and safety studies across the available anticoagulants, starting with warfarin and dabigatran and including additional ones as they become available within data sources available to us at the Division of Pharmacoepidemiology. Such sequential approach will extend Phase I analyses (study protocol 1160.157) by providing greater precision around effect estimates as well as providing an evaluation of their use in actual practice and among subgroups of patients that were not represented in clinical trials. This evaluation will provide a direct assessment of comparative effectiveness and potential adverse events across the anticoagulants that may have eluded the pre-marketing trials.

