13. ANNEX

ANNEX 1: LIST OF STAND-ALONE DOCUMENTS

None

Table A3 Follow-up and outcomes among matched cohorts

Group	Size	Follow-up (P-Y)	Outcome events	Incidence Rate	HR	95% CI
Dabigatran	N					
Warfarin	N					

[figure not shown]
This table will be repeated for each of the outcomes

Table A4 Follow-up and distribution of reasons for discontinuation

Group	Size	Follow-up (years)			Reasons for discontinuation (N, %)					
		Mean	Median	Max	Discontinue	Switch	Event	Disenrollment	Death	Nursing home admission
Dabigatran	N									
Warfarin	N									

This table will be repeated for each of the outcomes.

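### Table 8 gives stroke, a primary outcome, a lower base rate (31.59) than its ischemic component (32.71), which Table 2 does not allow

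*Combined protocol and SAP*

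**What the plan says.** Section 7.4.2 names the primary outcomes: "The primary outcomes of interest include stroke (hemorrhagic, ischemic, uncertain classification) and major bleeding". Table 2 in that section gives the codes, as primary discharge diagnosis. Stroke is 431.x and 433.x1 together with "434.x1 Occlusion and stenosis of cerebral arteries with cerebral infarction 436.x Acute, but ill-defined cerebrovascular events". The ischemic stroke row reads "As primary ICD-9 discharge diagnosis (Dx): ICD-9 Dx 433.x1 Occlusion and stenosis of precerebral arteries with cerebral infarction", followed by 434.x1.

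Section 7.7 gives the source of the base rates: "The base case incidence rates are the rates observed in warfarin initiators who were calendar quarter- and PS- matched to dabigatran initiators", for October 2010 to June 2012 in the UnitedHealth database. The footnote to Table 8 repeats this for the whole base-rate column: "Base rate is incidence rate per 1,000 Person-Years observed in warfarin initiators matched to dabigatran".

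In that column stroke is 31.59, while the ischemic row reads "Ischemic stroke 32.71". Hemorrhagic stroke is 2.09.

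**The concern.** Every event that counts as an ischemic stroke under Table 2 also counts as a stroke. A composite outcome cannot occur less often than one of its components in the same patients over the same period, yet Table 8 shows this.

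Stroke is one of two primary outcomes, and Table 8 is where the protocol states what effect it can detect for it at six interim reports and the final report. As printed, at least one of the two rows does not describe the outcome defined in Table 2. If the cause is a coding or labelling difference carried over from the pilot phase, it would be better found before outcomes are counted. The documents do not show that this is the cause.

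**Working it through.** **1. Can the composite rate be lower?** Take one cohort, as section 7.7 and the footnote state.

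- If follow-up does not stop at the event, person-time is the same for both outcomes and strokes are at least as many as ischemic strokes.
- If follow-up stops at the event (Table A4 lists the event among the reasons for stopping, with the note "This table will be repeated for each of the outcomes"), at least as many patients have a first stroke as have a first ischemic stroke. Person-time to first stroke is no longer than person-time to first ischemic stroke.

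In both cases the stroke rate is at least the ischemic rate. Table 8 shows a shortfall of 32.71 − 31.59 = 1.12 per 1,000 person-years. The rates are printed to 0.01, so rounding is not the reason.

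**2. Do the printed rows follow from the printed rates?** Inputs from Table 8 and section 7.7: two-sided alpha 0.05, 80% power, 1:1 matching, and 10,000 to 24,100 person-years. The abstract says the person-years are per group. The documents name no formula. I used the square-root formula for two rates:

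RR = (1 + (1.960 + 0.842) × √0.5 / √(rate × PY))²

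For stroke at interim report 1, rate × PY = 0.03159 × 10,000 = 315.9 and RR = (1 + 1.981/17.774)² = 1.235. For ischemic stroke, rate × PY = 327.1 and RR = (1 + 1.981/18.086)² = 1.231.

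| Report | PY | Stroke, at 31.59 | Printed | Ischemic, at 32.71 | Printed |
|---|---|---|---|---|---|
| Interim 1 | 10,000 | 1.235 | 1.24 | 1.231 | 1.23 |
| Interim 2 | 12,350 | 1.211 | 1.21 | 1.207 | 1.21 |
| Interim 3 | 14,700 | 1.192 | 1.19 | 1.189 | 1.19 |
| Interim 4 | 17,050 | 1.178 | 1.18 | 1.1748 | 1.17 |
| Interim 5 | 19,400 | 1.166 | 1.17 | 1.163 | 1.16 |
| Interim 6 | 21,750 | 1.157 | 1.16 | 1.154 | 1.15 |
| Final | 24,100 | 1.149 | 1.15 | 1.146 | 1.15 |

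The first stroke value is 1.2353 before rounding. All 14 cells match. The unpooled rate-difference form also matches all 14. Schoenfeld's formula misses one borderline stroke cell, and a Wald test on the log rate ratio misses one borderline ischemic cell.

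**3. Which base rates fit the printed rows?** Solving back from the rounded cells, the rates that fit all seven are 30.76–31.68 for stroke and 32.64–33.19 for ischemic stroke (square-root form). The rate-difference form gives 30.82–31.77 and 32.69–33.23. The ranges are disjoint under all four formulas. The printed rates were evidently the ones used, so a slip or extraction error in one base-rate cell does not explain the conflict.

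**4. Size.**

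- If 32.71 is right, stroke is at least 32.71 (32.71/31.59 = 1.035, so 3.5% above print). Its detectable rate is at most 1.231 at interim report 1 and 1.146 at the final report. At 32.71 exactly, the stroke row would fall by 0.01 in four of its seven cells (interim reports 1, 4, 5 and 6).
- If 31.59 is right, ischemic stroke is at most 31.59 (3.4% below print). Its detectable rate is at least 1.235 and 1.149.
- If only the labels are exchanged, the figures stand and the rows swap. The gap of 1.12 is then smaller than the hemorrhagic rate of 2.09, which requires that some patients had both types.
- Illustration, not a bound: if no patient had both types and code 436.x added nothing, stroke would be 32.71 + 2.09 = 34.80. RR would be (1 + 1.981/√348.0)² = 1.224 at interim report 1 and (1 + 1.981/√838.7)² = 1.141 at the final report, a move of about 0.01.

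**The case against.** **The consequence is negligible.** Study size is whatever the two databases yield, and Table 8 sets no sample size, stopping rule or analysis. The rates also fit small counts: 30/0.03159 = 950 and 31/0.03271 = 948 person-years, so the gap could be a single event. That is inference, since counts are not stated. A rate from 30 events has a 95% margin of roughly 1.96/√30 = 36%, far wider than 3.5%. All of this stands. It limits the weight of the point but does not make the two rows compatible.

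**The rates may be true Phase 1 results under another definition.** Phase 1 is a separate protocol: "Such sequential approach will extend Phase I analyses (study protocol 1160.157"). Neither section 7.7 nor the footnote says that the Table 2 codes were applied. This is a fair explanation and perhaps more likely than a mistyped rate. The footnote would then be incomplete rather than false, but the reader would still be shown a rate for something other than the outcome defined in Table 2.

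**The exact match depends on the formula.** This is correct. Under the log-rate-ratio Wald form, interim report 4 at 32.71 is 1.1752 and prints 1.18, so three stroke cells would change instead of four. The disjoint ranges do not depend on the choice.

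**The hemorrhagic stroke row has the larger discrepancy.** It does not reproduce from 2.09 under any of the four formulas: the square-root form gives 2.05 at interim report 1 against 1.87 printed, and the printed row implies a rate of about 2.9. That is a separate matter. It is why 34.80 is not used as a bound here.

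**Conclusion.** The point holds. Under the Table 2 definitions and the single cohort named in section 7.7, a stroke rate of 31.59 cannot stand beside an ischemic stroke rate of 32.71. A rate, the row labels, or the definition behind the footnote needs correcting, and the documents do not show which. The detectable relative rate for stroke moves by about 0.004 at interim report 1 and 0.003 at the final report at the strict bound, and by about 0.01 if the two stroke types do not overlap. These figures assume the printed person-years per group, 1:1 matching and the square-root formula. It is a table correction for a primary outcome and leaves the design as it is.

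**What to change.** Check the base rates and row labels for stroke and ischemic stroke against the Phase 1 output, applying the Table 2 codes and diagnosis position. Confirm that the stroke rate is at least as large as each of its components, then reissue the two rows. If Phase 1 used a different definition, either recompute under Table 2 or state that definition in the footnote. It would be sensible to check the hemorrhagic stroke row against the same output. The cost is a look-up of a few existing rates and an edit to two table rows or one footnote.
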